### **3                   3. ETHICAL CONSIDERATIONS**

#### **2.3 Good Clinical Practice**

This study will be conducted in accordance with Good Clinical Practice (GCP), as defined by the International Conference on Harmonisation (ICH) and in accordance with the ethical principles underlying European Union Directive 2001/20/EC and the United States Code of Federal Regulations, Title 21, Part 50 (21CFR50).

The study will be conducted in compliance with the protocol. The protocol, any amendments, and the subject informed consent will receive Institutional Review Board/Independent Ethics Committee (IRB/IEC) approval/favorable opinion before initiation of the study.

All potential serious breaches must be reported to Bristol-Myers Squibb (BMS) immediately. A serious breach is a breach of the conditions and principles of GCP in connection with the study or the protocol, which is likely to affect, to a significant degree, the safety or physical or mental integrity of the subjects of the study or the scientific value of the study.

Study personnel involved in conducting this study will be qualified by education, training, and experience to perform their respective tasks. This study will not use the services of study personnel where sanctions have been invoked or where there has been scientific misconduct or fraud (eg, loss of medical licensure; debarment). Systems with procedures that ensure the quality of every aspect of the study will be implemented.

#### **3.1               Institutional Review Board/Independent Ethics Committee**

Before study initiation, the investigator must have written and dated approval/favorable opinion from the IRB/IEC for the protocol, consent form, subject recruitment materials/process (eg, advertisements), and any other written information to be provided to subjects. The investigator should also provide the IRB/IEC with a copy of the Investigator Brochure or product labeling, information to be provided to subjects, and any updates. The investigator should provide the IRB/IEC with reports, updates, and other information (eg, expedited safety reports, amendments, and administrative letters) according to regulatory requirements or institution procedures.

### **3.2            Informed Consent**

Investigators must ensure that subjects (or, in those situations where consent cannot be given by subjects, the legally acceptable representative) are clearly and fully informed about the purpose, potential risks, and other critical issues regarding clinical studies in which they volunteer to participate. Freely given written informed consent must be obtained from every subject (or, in those situations where consent cannot be given by subjects, the legally acceptable representative) before clinical study participation, including informed consent for any screening procedures conducted to establish subject eligibility for the study. An additional informed consent form will be signed by subjects willing to supply DNA and RNA for research to predict response to abatacept.

The rights, safety, and well-being of the study subjects are the most important considerations and should prevail over interests of science and society.

### **3.4 Stopping Rules**

The study will be put on hold if 1) there are two deaths thought to be possibly, probably or definitely related to the treatment, or 2) there are 3 patients with SAEs thought to be probably or definitely related to the treatment. If either of these occurs, the study will be suspended until the DSMB determines whether it is safe for patients to continue on the therapy. This determination will be made within two weeks of the events described so that patients will hold their doses of abatacept or placebo for no longer than two weeks if the reviewers determine it is safe to continue. A data safety monitoring board (one to-be-named Rheumatology faculty member plus one to-be-named statistician) will review the SAEs quarterly and issue a report to the IRB and to the investigators regarding AEs and SAEs, reported according to patient assignments to groups A or B (the double-blind code will not be broken); these reports will also be supplied to the sponsor

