### **7.3 Collection and Reporting**

Adverse events can be spontaneously reported or elicited during open-ended questioning, examination, or evaluation of a subject. To prevent reporting bias, subjects should not be questioned regarding the specific occurrence of one or more adverse events.

If known, the diagnosis of the underlying illness or disorder should be recorded, rather than its individual symptoms. The following information should be captured for all AEs: onset, duration, intensity, seriousness, relationship to investigational product, action taken, and treatment required. If treatment for the event was administered, it should be recorded in the medical record. The investigator must supply BMS and the IRB/IEC with any additional information requested, notably for reported deaths of subjects.

Completion of supplemental CRFs may be requested for AEs and/or laboratory abnormalities that are reported/identified during the course of the study.

A data safety monitoring board (one to-be-named Rheumatology faculty member plus one to-be-named statistician) will review the SAEs quarterly and issue a report to the IRB and to the investigators regarding AEs and SAEs, reported according to patient assignments to groups A or B (the double-blind code will not be broken); these reports will also be supplied to the sponsor

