#### **7.3.1 Serious Adverse Events**

Following the subject's written consent to participate in the study, all SAEs must be collected, including those thought to be associated with protocol-specified procedures. Collection of all SAEs must continue for 30 days after the last administration of the investigational product. If applicable, SAEs must be collected that relate to any later protocol-specified procedure. The investigator should notify BMS of any SAE occurring after this time period that is believed to be related to the investigational product or protocol-specified procedure.

All SAEs, whether considered related or unrelated to abatacept, must be reported to BMS (by the investigator or designee) within 24 hours of study personnel becoming aware of the event. If only limited information is initially available, follow-up reports are required. The original SAE form must be kept on file at the study site.

All SAEs should be faxed or emailed to BMS at:

**Global Pharmacovigilance & Epidemiology  
Bristol-Myers Squibb Company  
[contact]  
Email: [contact]**

For studies conducted under an **Investigator IND**, any event that is both serious and unexpected must be reported to the Food and Drug Administration (FDA) as soon as possible **and no later than 7 days** (for a death or life-threatening event) **or 15 days** (for all other SAEs) **after the investigator's or institution's initial receipt of the information**. BMS will be provided with a simultaneous copy of all adverse events filed with the FDA. SAEs should be reported on MedWatch Form 3500A, which can be accessed at: <http://www.accessdata.fda.gov/scripts/medwatch/>.

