**All SAEs should simultaneously be faxed or e-mailed to BMS at:**

**Global Pharmacovigilance & Epidemiology  
Bristol-Myers Squibb Company  
[contact]  
Email: [[contact]](mailto:[contact])**

Serious adverse events, whether related or unrelated to abatacept, must be recorded on the SAE page and reported within 24-hours to BMS (or designee) to comply with regulatory requirements. An SAE report should be completed for any event where doubt exists regarding its status of seriousness.

All SAEs must be reported within 24-hours by confirmed facsimile transmission (fax) and mailing of the completed SAE page. In some instances where a facsimile machine is not available, overnight express mail may be used. If only limited information is initially available, follow-up reports are required. (Note: Follow-up SAE reports should include the same investigator term(s) initially reported.) In selected circumstances, the protocol may specify conditions that require additional telephone reporting.

If the investigator believes that an SAE is not related to the investigational product but is potentially related to the conditions of the study (such as withdrawal of previous therapy, or a complication of a study procedure), the potential relationship should be specified in the narrative section of the SAE report.

If an ongoing SAE changes in its intensity or relationship to the investigational product, a follow-up SAE report should be sent within 24 hours to BMS. As follow-up information becomes available it should be sent within 24 hours using the same procedure used for transmitting the initial SAE report. All SAEs should be followed to resolution or stabilization.

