## **8 STATISTICAL CONSIDERATIONS**

### **8.1 Sample Size Determination**

We based our sample sizes on the preliminary data (unpublished): SLE patients with arthritis at the start of a treatment had a mean score on 66-joint count of  $21 \pm 8.2$ . There was a decrease to a mean of  $2.0 \pm 1.5$  after 12 weeks of various interventions in patients who reported they improved. For the study proposed here, if 67% of abatacept pts will achieve 20% improvement in swollen and tender joints vs. 30% of controls by week 16, n=28 per group (with p=0.05, power=0.8). Thus we plan 32 patients for abatacept over 16 weeks and 32 patients for placebo over 16 weeks, a total of 64. The dropout rate in the abatacept non-nephritis lupus trial was 35% (over 12 months). We anticipate one-third that in a 4 month trial, proposed, here – i.e. 12%. If we begin with 64 patients we should have 56 completers, thus approximately 28 in each group.

Thus, we will plan to recruit 32 SLE patients at UCLA and an additional 32 at UCSD (separate contract).

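### The stopping rule needs a DSMB determination within two weeks, but no written route sends individual SAEs to the DSMB or keeps one count across the two sites

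*Combined protocol and SAP*

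**What the plan says.** Section 3.4 (Stopping Rules) sets two study-wide triggers. The first is met when "there are two deaths thought to be possibly, probably or definitely related to the treatment". The second is met when "there are 3 patients with SAEs thought to be probably or definitely related to the treatment". In either case "the study will be suspended until the DSMB determines whether it is safe for patients to continue on the therapy", and on timing: "This determination will be made within two weeks of the events described". The same sentence uses that limit to cap how long patients hold their doses.

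Sections 3.4, 6.3 and 7.3 then describe the DSMB's routine work in the same words: it "will review the SAEs quarterly and issue a report to the IRB and to the investigators regarding AEs and SAEs". No other DSMB input is described.

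Individual SAEs follow a different route. Section 7.3.1 states: "All SAEs, whether considered related or unrelated to abatacept, must be reported to BMS (by the investigator or designee) within 24 hours". It repeats this further on: SAEs "must be recorded on the SAE page and reported within 24-hours to BMS". Serious unexpected events also go to the FDA, within 7 or 15 days.

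Two other provisions bear on the point. Section 6.1 and its schedule have staff check at weeks 4, 8, 12 and 16, and at early termination, whether the stopping rules have been met. Section 7.3.2 has BMS notify investigators of SAEs that are both suspected and unexpected.

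Section 8.1 plans 32 patients at each of two sites, the second under a separate contract.

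**The concern.** The triggers count events over both sites, and the two-week limit runs from the events themselves. The rule therefore works only if someone sees the combined count almost at once and tells the DSMB. The text names nobody to do either, and nobody to declare the hold.

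Suppose UCLA has two patients with qualifying SAEs and UCSD has one. The trigger is met, but each site's own records fall short of three. BMS holds all three reports within 24 hours, yet Section 3.4 gives BMS no part in the rule. Followed as written, the procedures can leave patients self-injecting at home, and new patients starting, after the pausing criterion has been reached.

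The count is also hard to make. Section 3.4 uses possible, probable and definite relationship, with a different threshold for deaths than for SAEs. Section 7.2 records only Related or Not Related, so the recorded data do not show which events count.

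**Working it through.** The two-week limit is a procedural promise, so there is no computed figure to reproduce. The check sets the written routes against it and then works out the timing.

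**Who learns of an individual SAE, and when**
- BMS: all SAEs within 24 hours of site awareness (7.3.1). No assigned role in the 3.4 rule.
- FDA: serious and unexpected events, within 7 or 15 days (7.3.1).
- IRB: reports under regulatory requirements or institutional procedure (3.1), and further information on request (7.3).
- Investigators: suspected and unexpected SAEs, through BMS (7.3.2). BMS may also circulate a raised frequency of a significant expected SAE, but this is discretionary. Section 1.4 already lists serious or fatal infections as a risk, so such an SAE may be classed as expected and fall outside the required notice.
- Site staff: a stopping-rule check at each 4-weekly visit (6.1). No text gives a site the other site's count between quarterly reports.
- DSMB: quarterly review only (3.4, 6.3, 7.3).

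**Waiting time if the DSMB learns only at its review**
- One quarter = 52/4 = 13 weeks, against a limit of 2 weeks and a 16-week course (4.1).
- Range 0 to 13 weeks. The worst case is 13/16, or about 81% of a course, and 13 − 2 = 11 weeks past the limit.
- If triggers fall uniformly between reviews (assumption), the mean wait is 13/2 = 6.5 weeks, about 41% of a course. The next review falls within two weeks for 2/13 = 15% of triggers.

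**How often a trigger would involve both sites**
Assume equal risk in all 64 patients, 32 per site.
- Three patients: 1 − 2·C(32,3)/C(64,3) = 1 − 9,920/41,664 = 76%.
- Two deaths: 32 × 32/C(64,2) = 1,024/2,016 = 51%.

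**New patients starting in one quarter**
- At the Synopsis rate of 2–3 per month per site: 2 sites × 2–3 × 3 months = 12–18.
- If 64 patients are spread over the Synopsis window of April 2015 to March 2018 (36 months): 64/36 = 1.8 per month, or about 5 per quarter.
- Range: about 5 to 18.

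**How likely the SAE trigger is at all**
The documents give no rate for SAEs judged at least probably related, so this is illustrative. If each of 64 patients has a 2% chance of a qualifying SAE, the binomial probability of three or more is 14%. At 5% it is 63%. The 2% matches 2 of 100 abatacept-treated patients in the RA study IM101173 (1.3.4). That figure counts at least possibly related SAEs, a wider class than the trigger, and is applied here to both arms.

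**The case against.** The strongest reply is that Section 3.4 contains two separate mechanisms. One is event-driven: a trigger suspends the study and the DSMB decides within two weeks. The other is routine quarterly review. A reader might infer that the quarterly review is the hold mechanism and so cannot meet the limit. The text does not support that, because it plainly intends an unscheduled determination. What is missing is the written step that sets it in motion.

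A reader might also infer that no individual SAE ever crosses between sites. That is not so: the BMS notices in 7.3.2 carry suspected unexpected SAEs to investigators, and such events are likely to feed the trigger. Nor is a met trigger necessarily unseen by everyone. Section 6.1 has each site check the rules at every visit, which can catch a trigger reached within one site. BMS has both sites' reports within 24 hours, can terminate the study (4.4), and may temporarily halt a study for safety reasons (7.3.2).

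These replies narrow the point without closing it. The required notices do not cover expected SAEs and do not name the DSMB. The visit checks do not give a site the other site's count. BMS's general powers are not tied to the 3.4 triggers. Section 7.3.1 allows that a protocol may specify additional telephone reporting, but no such condition appears in the text available. Part of the SAE-reporting section and the contract for the second site are outside that text and could contain a route. If so, 3.4 should point to it.

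**Conclusion.** The concern holds in a limited form. The protocol intends a prompt DSMB decision, but the reporting routes in the text available do not ensure one when a trigger is split across UCLA and UCSD, especially by expected SAEs. Such a trigger can go unrecognised by the DSMB and the sites until the next quarterly review.

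The 0 to 13 weeks, and the mean of 6.5, rest on the DSMB learning only through that review; the mean also needs uniform timing. A reader might take the delay to be most of a treatment course as a rule. That is the worst case only. The figure of 5 to 18 new starts depends on which of the Synopsis accrual figures is used and applies to a full quarter's wait. The 76% and 51% assume equal risk per patient. The gap itself depends on none of these numbers.

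The mismatch between the causality terms in 3.4 and 7.2 is a separate contradiction. It must be reconciled before any trigger can be counted reliably. This should be changed: it concerns the trial's explicit safety stop, and the remedy is small.

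**What to change.** - In 3.4 and 7.3.1, send every death and every SAE, with its causality assessment and without treatment code, to both DSMB members and the other site's investigator on the 24-hour clock already used for BMS.
- Name one role that keeps the cross-site count, notifies the DSMB that a trigger is met, and declares the hold.
- Reconcile the causality terms in 3.4 with the scale in 7.2 so that the recorded data show whether an event counts.
- Leave the triggers unchanged and the two-week limit counted from the events. Restarting the clock at the declaration might look tidier, but it would rewrite the hold limit, and late recognition would no longer breach it.
- Keep the quarterly review for routine monitoring.

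If the site learns of the last qualifying event on the day it occurs, the DSMB has it about one day later, with about 13 of the 14 days left.

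The cost is a recipient line on the SAE form and a few protocol sentences, with no new staff. The number of messages should be small. Scaling the 19.8% SAE incidence over 12 months on abatacept in the earlier SLE trial (1.3.4) in proportion to time gives 19.8% × 16/52 = 6.1%, or about 4 patients in 64. The downside is that each site learns of the other's SAEs, without treatment code.

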Study Design:	Randomized trial of 32 SLE patients treated with subcutaneous abatacept 125mg sq once a week vs. 32 placebo treated subjects over a 16 week period. Patients will be seen every 4 weeks from baseline. One half of patients will be recruited at UCLA and one-half at UCSD. We expect 30 patients in each group to complete the 16 week study.
Study Schema Drugs / Doses / Length of Treatment)	Abatacept 125 mg or placebo will be administered subcutaneously once a week for 16 weeks. There will be a telephone follow up 2 months after the last injection to capture post-treatment adverse events.
Accrual Goal: (Total number of subjects)	64 (32 at UCLA and 32 at UCSD)
Accrual Rate: (Number of subjects expected per month)	2-3 subjects per month at each site
FPFV: April 1, 2015 LPFV: March 31, 2018  Follow Up: 16 weeks per patient plus 8 weeks of observation for adverse events	
Correlative Studies: These will be performed at the UCLA site only	
1) Biomarkers: a) T cell numbers and phenotypic and functional characteristic in PBMC measured at week 0 and 16. These will include for T cells CD4+, CD3+, CD25+, CD8+, Foxp3+ and cytoplasmic stains for IFNgamma, IL2, IL-17, IL21 and IL-10.
 
b) B cell numbers and subsets, including naïve, activated and plasmablasts.
 
c) Ability of autologous CD4+CD25hi T cells to suppress proliferation of CD4+CD25- T cells.
 
d) Cytokines in serum: IFNgamma, IL-6, IL-10, IL-17, IL23 and BLyS
 
2) Ultrasound with power Doppler of joints assessing synovitis, tenosynovitis (18 joints) and erosions at week 0 and 16.

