#### **4.2.3 Discontinuation of Subjects from Treatment**

If a study subject is found to have worsening disease activity during the duration of the study, the choice of using a rescue medication (e.g. increase prednisone dose but not to  $>20$  mg daily) will be considered. However, if significant worsening of disease activity is found at 8 weeks in comparison to baseline disease activity, the investigator will consider the discontinuation of the subject from the study after discussing in detail with the patient alternative SLE treatment strategies. Throughout the duration of the study, background allowed standard of care therapies (prednisone, MMF, leflunomide, hydroxychloroquine) will be continued at the baseline dosage.

Subjects MUST discontinue study treatment and withdraw from the study for any of the following reasons:

- Withdrawal of informed consent (subject's decision to withdraw for any reason)
- Any clinical adverse event (AE), laboratory abnormality, or intercurrent illness which, in the opinion of the investigator, indicates that continued participation in the study is not in the best interest of the subject
- Pregnancy
  - Instruct WOCBP to contact the investigator or study staff immediately if they suspect they might be pregnant (eg, missed or late menstrual period) at any time during study participation. Institutional policy and local regulations should determine the frequency of on-study pregnancy tests for WOCBP enrolled in the study.
  - The investigator must immediately notify BMS if a study subject becomes pregnant. The mechanism for reporting pregnancy is described in Section 7.6.
- Termination of the study by BMS
- Loss of ability to freely provide consent through imprisonment or involuntarily incarceration for treatment of either a psychiatric or physical (eg, infectious disease) illness

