#### **5.4 Blinding/Unblinding**

No data will be unblinded until the conclusion of the study, unless a serious adverse event cannot be treated effectively without the information, or unless 2 or more deaths that may be related to the therapy occur.

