## **6.3 Safety Assessments**

All subjects who receive a dose of study drug will be evaluated for safety. Safety outcomes include adverse events, clinically significant changes in vital signs, laboratory test abnormalities, and clinical tolerability of the drug. The investigator will determine the severity of each adverse event as mild, moderate, severe, or very severe. Laboratory findings that the investigator feels are clinically relevant should be recorded as adverse events. In addition, the investigator will determine the relationship of the adverse event to the administration of the study drug. Any occurrence of a SAE from time of consent forward, up to and including follow-up visits will be reported. A data safety monitoring board (one to-be-named Rheumatology faculty member plus one to-be-named statistician) will review the SAEs quarterly and issue a report to the IRB and to the investigators regarding AEs and SAEs, reported according to patient assignments to groups A or B (the double-blind code will not be broken); these reports will also be supplied to the sponsor. See Section 7.3.1 for the SAE reporting procedures.

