### **Physician Global Assessment**

Physician Global Assessment is a Visual Analogue Scale. It measures the disease activity based on the physician subjective assessment from none active to worse disease activity. PGA will be performed at every visit (except for screening)

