#### **7.2            *Assignment of Adverse Event Intensity and Relationship to Abatacept***

All adverse events, including those that are serious, will be graded by the investigator as follows:

- Mild (Grade 1): awareness of event but easily tolerated
- Moderate (Grade 2): discomfort enough to cause some interference with usual activity
- Severe (Grade 3): inability to carry out usual activity
- Very Severe (Grade 4): debilitating; significantly incapacitates subject despite symptomatic therapy.

The following categories and definitions of causal relationship to investigational product as determined by a physician should be used:

- **Related:** There is a reasonable causal relationship to investigational product administration and the adverse event.
- **Not Related:** There is not a reasonable causal relationship to investigational product administration and the adverse event.

The expression “reasonable causal relationship” is meant to convey in general that there are facts (eg, evidence such as de-challenge/re-challenge) or other arguments to suggest a positive causal relationship.

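### Quarterly AE/SAE reports split by group A/B go to the investigators while patients are still being rated: a small, avoidable risk to the blind

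*Combined protocol and SAP*

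**What the plan says.** Section 3.4 (Stopping Rules) sets up a two-member DSMB that reviews SAEs each quarter and is to "issue a report to the IRB and to the investigators regarding AEs and SAEs, reported according to patient assignments to groups A or B". The sponsor also receives the report. Section 6.3 repeats the arrangement with its one safeguard: "reported according to patient assignments to groups A or B (the double-blind code will not be broken". Section 7.3 carries the same wording a third time. No section provides a version of the report for the DSMB alone or a pooled version for the sites.

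Section 5.4 protects the code: "No data will be unblinded until the conclusion of the study". It allows two exceptions: an SAE that cannot be treated effectively without the information, and two or more possibly related deaths.

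The report recipients also judge patients. Section 7.2 says: "All adverse events, including those that are serious, will be graded by the investigator as follows". Section 6.4 says of the Physician Global Assessment: "It measures the disease activity based on the physician subjective assessment". The primary endpoint (Section 6.4.1) rests on tender and swollen joints found on examination, and Section 4.1 schedules these counts every 4 weeks. Section 6.4 does not say who performs them. Section 1.2.2 only remarks that experienced investigators can quantify lupus arthritis.

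The Synopsis gives the planned accrual as "2-3 subjects per month at each site" and the enrolment window as "FPFV: April 1, 2015 LPFV: March 31, 2018".

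**The concern.** Sealing the code hides what A and B stand for. It does not hide that one letter has more events than the other. It also does not hide which letter a recognisable patient carries, if a report describes events in enough detail and the letters keep their meaning from one report to the next. An investigator who graded an unusual event would know whose it was.

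If that person also counts joints or scores the physician global, a guess about the arm could colour ratings that depend on judgement. At stake is the credibility of an examiner-rated primary endpoint in a 64-patient trial. Comparing the groups for safety needs the split tables only at the DSMB.

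**Working it through.** The plan gives no figure for this risk, so there is none to reproduce. Sample size, alpha and power are not affected. The check asks how many patients could be both linked to a letter and still unrated, and how much the letter would tell.

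**Step 1. Do reports arrive during assessment?** Reports come about every 13 weeks and treatment lasts 16 weeks, or 3.68 months. Two sites at 2-3 patients per month give 4-6 per month. Reports before the last week-16 visit, counted quarterly from the first patient (assumed):
- 6 per month: (64/6 + 3.68)/3 = (10.7 + 3.68)/3 = 4.8, so 4 reports.
- 4 per month: (64/4 + 3.68)/3 = (16 + 3.68)/3 = 6.6, so 6 reports.
- Enrolment filling the 36-month window: (36 + 3.68)/3 = 13.2, so up to 13 reports.

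**Step 2. How many SAE patients are expected?** The 12-month lupus trial summarised in the background had SAEs in 19.8% (abatacept) and 6.8% (placebo). Scaled to 16 weeks at constant hazard (assumed), 1 - (1 - r)^(16/52):
- 19.8% becomes 6.56%.
- 6.8% becomes 2.14%.
- Expected SAE patients: 32 x 0.0656 + 32 x 0.0214 = 2.79 (from unrounded rates).

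Alternative: the same background section quotes 2% for the 16-week subcutaneous RA study. Applied to both arms (assumed), 64 x 0.02 = 1.28. This is probably a floor, because Section 1.3.4 describes the 2 subjects in that study as those with at least possibly related SAEs.

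**Step 3. What share is reported before the patient's own week-16 visit?** Assume SAE time uniform over 3.68 months.
- Report delay uniform over 0-3 months: (1.5 + 0.68)/3.68 = 59.2%.
- Delay uniform over 1-4 months (one month of preparation): (2.68^2/6)/3.68 = 32.5%.

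Patients exposed:
- 19.8% vs 6.8%: 2.79 x 0.325 to 2.79 x 0.592 = 0.91 to 1.65.
- 2% in both arms: 1.28 x 0.325 to 1.28 x 0.592 = 0.42 to 0.76.

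Withdrawal after an SAE would lower both.

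**Step 4. How well do SAE counts reveal the letter?** Independent binomials with 16 completed patients per arm:

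| Rates | Abatacept more | Tie | Abatacept fewer | Difference (more - fewer) |
|---|---|---|---|---|
| 6.56% vs 2.14% | 0.542 | 0.341 | 0.117 | +0.425 |
| 2% vs 2% | 0.209 | 0.581 | 0.209 | 0 |

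Under the first row, abatacept leads by two or more patients in only 22%.

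**Step 5. Combine.** Wrong guesses push ratings the other way, so the difference is a fair rough weight. Treating linkage and clue as independent (assumed):
- 19.8% vs 6.8%: 0.91 x 0.425 to 1.65 x 0.425 = 0.4 to 0.7 patients in the whole trial.
- 2% in both arms: about zero.

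Sensitivity to timing under the first row of rates: at 8 per arm the difference is 0.366 - 0.096 = 0.27, giving 0.2 to 0.4 patients. At 32 per arm it is 0.710 - 0.105 = 0.605, but by then everyone has been rated.

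**The case against.** The strongest reply is that the protocol contains no error here. Reports carry letters only, the text says three times that the code is not broken, and Section 5.4 backs this up. Harm needs several things together: detailed reports, persistent labels, a recipient who also counts joints, and a correct guess about the letter. The first three are not stated. If reports give bare counts, the link to an individual is weak. All of this stands, and it is why the point is a small one.

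Four stronger readings are tempting, and the documents do not support them.

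- **That the reports break the blind or contradict Section 5.4.** They do not. Coded letters and a sealed code are compatible. An emergency code break could decode the letters, but the plan gives no frequency for it, so it carries no weight here.
- **That everyone on treatment is at risk.** At planned accrual 4 x 3.68 to 6 x 3.68, or about 15 to 22 patients, are on treatment at once. Only those both linkable and not yet rated are exposed.
- **That the nephritis trial's SAE rates (28-33.3% vs 31%) set the upper end.** They would give 2.1 to 4.3 exposed patients. However, active nephritis is excluded here, the background section calls the non-nephritis patients the most comparable, and such similar arm rates carry almost no clue (difference -0.08 to +0.06).
- **That week-8 withdrawals could be steered.** Section 4.2.3 says "the investigator will consider the discontinuation of the subject from the study", but only after significant worsening. Under 19.8% vs 6.8%, the share reported before the patient's own week-8 visit is 3.2% to 15.3%, or 0.1 to 0.4 patients (2.79 x 0.032 to 2.79 x 0.153), before that further condition applies. This is negligible.

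A fair objection on cost also stands. The change is not free of procedure: Section 3.1 makes the investigator the usual channel for reports to the IRB, so coded tables for the IRB would need another route.

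**Conclusion.** The point holds as a cheap improvement to consider. The plan sends group-split safety tables to people who may be rating outcomes, and the sealed code is only a partial safeguard.

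The size rests on constant-hazard scaling, uniform SAE timing, a report delay of 0-3 or 1-4 months, 16 completed patients per arm, and independence of linkage and clue. It also supposes that reports are detailed enough to recognise a patient and that labels persist. That the recipients count joints is an inference, because no section assigns the task. Non-serious AEs are in the reports too and could add exposure, but the documents give no rate, so none is estimated.

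**What to change.** Amend Sections 3.4, 6.3 and 7.3 together:

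- A/B tables go to the DSMB only.
- Investigators, and anyone who assesses patients, receive AE/SAE counts pooled over both groups plus the DSMB's recommendation. This wording covers the joint assessor, whoever that is.
- The IRB and sponsor receive the pooled report, or coded tables sent directly by the DSMB and not shared with site staff.

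Individual SAE reporting and the hold triggers stay as they are.

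Cost: wording in three places, two versions of each quarterly report, and a direct DSMB route if the IRB or sponsor is to hold coded tables. Sites would see safety counts by group only at study end; the DSMB would still see them throughout.
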